5.2. Randomization Procedures

Participants will be randomized in a 1:1 allocation to either: a) the mobile intervention of PrEP iT! in addition to usual care, or b) a control condition that consists only of usual care. The randomization sequence will be stratified by age (18-24 v. 25-29 yrs) and use blocks of four. Given the nature of the intervention, treatment allocation will not be blinded following randomization.

All study staff and participants will be unaware of randomized group allocation until enrollment and randomization procedures are completed. Following screening and enrollment, participant eligibility will be re-confirmed. After completion of the randomization CRF, the treatment allocation will be revealed within the study database. Research staff will

then instruct participants on their study group, and participants within the mobile intervention arm will be guide through setup of the PrEP iT! web application.

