2.4. Recruitment

Participants will be recruited from clinical settings where PrEP care is delivered as well as via social media advertisement that targets potential PrEP users within the MSM community. In Minneapolis, specific settings that will be a focus of recruitment efforts include the Hennepin County Public Health clinic ('Red Door' clinic), the Hennepin Healthcare HIV clinic ('Positive Care Center') as well as HIV prevention organizations within the Twin Cities (e.g., Youth AIDS Project). Recruitment and enrollment of study participants will be concurrent with their PrEP clinical visits when possible, or online via a HIPPA-compliant teleconferencing platform such as Zoom. Whether recruited within these facilities or via social media advertisements, HHRI research staff will interview candidate participants to assess for potential eligibility. Following this, interested participants will undergo informed consent procedures, both verbal and written, followed by screening visit to verify eligibility. Additional detail outlining participant recruitment, including digital and paper recruitment materials, is provided in the study MOP.

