5. STATISTICAL METHODS

5.1. Sample Size Considerations

The sample size for this proof-of-concept study (n=40 per group; n=80 total) is consistent with recommendations of sample sizes for pilot studies of this nature.²² Power calculations are presented for the two adherence outcomes: TFV-DP levels and the adherence score. For the TFV-DP levels (n=20 in each arm), prior research suggests that approximately 40% will have levels TFV-DP levels >700 fmol/punch at 3 months. Assuming a type I error of 5% and using a chi-square test statistic, we have 80% power to detect a relative risk of 2.0 or larger (i.e., that the intervention group is 2.0 times as likely to have high levels of TFV-DP as the control group). Adherence may decrease by 6 months, increasing our detectable effect. If we assume 30% adherence at 6 months, we have 80% power to detect a relative risk of 2.4 or higher. For the adherence score derived from Wilson et al.'s²³ 3-item measure, prior research on ART therapy suggests a standard deviation of approximately 20.²³ Assuming we will see the same standard deviation among PrEP users and a type-1 error rate of 5%, we have 80% power to detect a difference in adherence scores of 12.7 units between the two groups. This is approximately half of a standard deviation change, and should provide good preliminary evidence to inform future trials.

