5.3. Analysis Plan

Feasibility of delivering the intervention will be assessed by examining the percentage of eligible people who are successfully recruited into the study and by the percentage of participants retained at each visit. Chi-square tests (or Fisher's exact test, for small cell counts) will be used to compare the intervention and control groups in the proportions of participants retained at both 3- and 6-month follow-up. We will use the following retention cut-off percentages to assess feasibility: a) 90+ = strong feasibility; b) 80-89% = acceptable feasibility; c) 70-79% = modest feasibility with a need for improvement; d) <70% = unacceptable feasibility.

Acceptability will be measured using a 10-item self-report System Usability Scale (SUS)²⁴ computed in the intervention arm over time (at 3- & 6-months). The average SUS score across 400 studies was 68²⁴ (possible range 0-100); therefore, an average score of ≥ 68 will be considered acceptable and ≥ 80 highly acceptable. We will estimate overall acceptability and changes over time. Acceptability will further be assessed by recording the frequency of *PrEP iT!* interaction (average number of uses per week) over follow-up time.

The preliminary impact of the mobile intervention will specifically be evaluated. We will focus on two adherence measures to estimate the preliminary efficacy of the *PrEP iT!* intervention. Objective adherence will be assessed via TFV-DP levels in DBS samples ($n \geq 20$ per treatment arm). TFV-DP data will be dichotomized into high levels (≥ 700 fmol/punch) vs low levels (< 700 fmol/punch) and the difference in proportion of high levels of TFV-DP between treatment arm will be estimated using chi-square or Fisher's exact test at both 3 and 6 months. In a separate analysis, we will keep TFV-DP as a continuous variable and examine differences between control and intervention groups using T-tests and permutation tests. Second, at 3 and 6 months, we will use the validated 3-item self-report adherence measure developed by Wilson and his colleagues.²³ T-tests will compare the mean adherence score between intervention and control arm at 3 and 6 months. Permutation tests will also be used to test for treatment group differences, since they do not require distributional assumptions and are typically more robust.

6. REFERENCES:

1. Centers for Disease Control and Prevention. HIV Surveillance Report, 2016. 2017.

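### Fixed blocks of four in an open-label trial would let staff who keep count know about one in three allocations in advance; vary the block size and withhold the order

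*Combined protocol and SAP*

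**What the plan says.** Section 5.2 (Randomization Procedures) sets 1:1 allocation and states: "The randomization sequence will be stratified by age (18-24 v. 25-29 yrs) and use blocks of four". It adds that "treatment allocation will not be blinded following randomization". On concealment it promises: "All study staff and participants will be unaware of randomized group allocation until enrollment and randomization procedures are completed". Eligibility is re-confirmed, the randomization form is completed, and the study database then shows the assignment. Research staff "then instruct participants on their study group" and help the intervention group set up the application.

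Section 2.4 (Recruitment) gives research staff the front-end role as well: "HHRI research staff will interview candidate participants to assess for potential eligibility". Age is an inclusion criterion (section 2.3), so the stratum is known before randomization. Neither section 5.2 nor any other section says that block sizes vary or that the size is withheld from enrolling staff.

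**The concern.** Hiding the next database entry conceals that entry. It does not stop someone working it out from earlier assignments, which are openly known here. Three things make this easy: the block size is printed in the protocol, there are only two running counts to keep, and the staff who deliver the assignment also assess candidates. For the allocations that can be deduced, the promise that staff are unaware until randomization is complete is not secured.

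Foreknowledge would act through whom staff approach and when they complete an enrolment. The results exposed are those that depend on which arm a person joins:

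- the retention analysis in section 5.3, which will "compare the intervention and control groups in the proportions of participants retained at both 3- and 6-month follow-up";
- the usability score, which is measured in the intervention arm only;
- both adherence comparisons.

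Pooled retention is little affected, because moving a candidate between arms does not by itself change the total. Section 2.1 says the design was chosen to rehearse the later efficacy trial, so the procedure may be carried forward to a setting where bias costs more.

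**Working it through.** The plan gives no predictability figure to reproduce. The one plan figure used as a yardstick is in section 5.1: "we have 80% power to detect a difference in adherence scores of 12.7 units between the two groups". With 40 per arm, SD 20 and a two-sided 5% t-test, power at 12.7 units is 80.1%, so that figure reproduces.

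**Inputs.** Block size 4, 1:1, two age strata, 80 participants (sections 5.1 and 5.2). SD 20 (section 5.1). The split between age strata is not given, so it was varied.

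**Certain allocations.** A block holds two places per arm, giving 6 equally likely orders. An allocation is certain once one arm's two places are used.

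- Probability of certainty at positions 1 to 4: 0, 0, 1/3, 1.
- Expected number per block: 4/3, so the share is (4/3)/4 = 33.3%. This is a long-run average; a single block exposes one or two of its four.
- In 80 participants with complete blocks: 80/3 = 26.7. With a 38/42 split, 9 complete blocks give 12.0 and 10 give 13.3, and the two leftover places in each stratum add none: 25.3. Splits from 10/70 to 70/10 give 25.3 to 26.7.

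**Best guess.** Guessing the arm with more places left is right with probability 1/2, 2/3, 2/3, 1 at positions 1 to 4. The mean is 2.833/4 = 70.8%, against 50% by chance.

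**From foreknowledge to bias.** Suppose that steering raises a participant's expected outcome by h SD when the intervention is expected and lowers it by h SD when control is expected. The documents give no h; 0.1 to 0.25 is assumed.

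- (a) Steering on every certain allocation and on no other: a third of each arm is shifted, in opposite directions, so bias = 2 × 1/3 × h = 0.67h.
- (b) Steering on every best guess, with wrong guesses cancelling right ones: bias = 2 × (2 × 0.708 − 1) × h = 0.83h.

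**Alternatives.** These were simulated with 40 allocations per sequence, block sizes drawn at random, and a tracker who knows the set of sizes but not their order.

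| Block sizes | Certain | Best guess right | Bias (a) | Bias (b) |
|---|---|---|---|---|
| 4 only (plan) | 33.3% | 70.8% | 0.67h | 0.83h |
| 4, 6 | 5.7% | 69.0% | 0.11h | 0.76h |
| 2, 4, 6 | 4.0% | 70.0% | 0.08h | 0.80h |
| 4, 6, 8 | 2.3% | 67.6% | 0.05h | 0.71h |

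Repeat runs agree to within about 0.1 to 0.2 percentage points and 0.01h.

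**In adherence-score units** (factor × h × 20, with h from 0.1 to 0.25):

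- (a) Plan: 0.67 × 2 = 1.3 to 0.67 × 5 = 3.3 units, which is 10 to 26% of 12.7. Sizes 4, 6, 8: 0.1 to 0.2 units, 1 to 2%.
- (b) Plan: 1.7 to 4.2 units. Sizes 4, 6, 8: 1.4 to 3.5 units, about 15% lower.

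**Price in balance.** With sizes 4, 6 and 8, the largest possible imbalance rises from 2 to 4 per stratum, so from 4 to 8 overall. In 20,000 simulated trials of 80 (20 to 60 in one stratum), mean absolute imbalance rose from 0.76 to 1.06 participants. The chance of an imbalance of 4 or more rose from 1.4% to 4.2%.

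**The case against.** Fixed blocks of four are a legitimate design, and nothing in the plan suggests that staff will keep count. Someone who did so in order to steer would probably act on likely allocations as well as certain ones. Against that person the fix gains little: 0.83h to 0.71h, or roughly 0.25 to 0.6 units, when the standard error of the comparison is 20 × √(2/40) = 4.5 units. This stands, and it is why the benefit should be described as removing certainty and not as removing predictability.

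The 10 to 26% figure needs both an assumed h and full use of every certain allocation. If a quarter of the opportunities were used (again an assumption), case (a) becomes 0.17h, which is 0.3 to 0.8 units or 3 to 7% of 12.7. This stands too: the larger figure is a ceiling for case (a). The unit figures also concern a secondary outcome. Of the primary outcomes, pooled retention is barely touched, and the effect on the usability score was not quantified.

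Other safeguards exist: self-directed online screening, checks against the medical record, consent and the baseline survey before randomization, and re-confirmed eligibility. They limit who qualifies and what can be done after consent. They do not settle whom staff approach or when an enrolment is completed.

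The Manual of Operating Procedures was not available and might hold randomization detail. Section 5.2 does not refer to it, however, and as written the rule reads as fixed blocks of four.

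**Conclusion.** The concern holds. For staff who know the block size and the strata and track every assignment, a third of allocations on average are known in advance, so the concealment that section 5.2 promises is not secured for them. The 33.3% and 70.8% are exact for complete blocks. The translation into bias is conditional on h and on how often foreknowledge is used, neither of which the documents give. This is a weakness of procedure with a cheap remedy: worth correcting, but not a threat to what the pilot can show about feasibility.

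**What to change.** In section 5.2, replace the fixed block size with wording such as: *permuted blocks of randomly varying size (4, 6 and 8) within age strata; the order of block sizes is held in a restricted document by a person with no part in enrolment and is not disclosed to enrolling staff*. Load the new table into the study database. Naming the set of sizes is acceptable, because the 2.3% already assumes that staff know it; the order is what must be withheld. Sizes 2, 4 and 6 are a weaker choice, as the table shows.

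The cost is one sentence, one regenerated table and the small loss of balance given above. Sample size, visits and analyses do not change. If enrolment has already begun, switch in each stratum at the end of a completed block and record the date.

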5.3. Analysis Plan

Feasibility of delivering the intervention will be assessed by examining the percentage of eligible people who are successfully recruited into the study and by the percentage of participants retained at each visit. Chi-square tests (or Fisher's exact test, for small cell counts) will be used to compare the intervention and control groups in the proportions of participants retained at both 3- and 6-month follow-up. We will use the following retention cut-off percentages to assess feasibility: a) 90+ = strong feasibility; b) 80-89% = acceptable feasibility; c) 70-79% = modest feasibility with a need for improvement; d) <70% = unacceptable feasibility.

Acceptability will be measured using a 10-item self-report System Usability Scale (SUS)²⁴ computed in the intervention arm over time (at 3- & 6-months). The average SUS score across 400 studies was 68²⁴ (possible range 0-100); therefore, an average score of ≥ 68 will be considered acceptable and ≥ 80 highly acceptable. We will estimate overall acceptability and changes over time. Acceptability will further be assessed by recording the frequency of *PrEP iT!* interaction (average number of uses per week) over follow-up time.

The preliminary impact of the mobile intervention will specifically be evaluated. We will focus on two adherence measures to estimate the preliminary efficacy of the *PrEP iT!* intervention. Objective adherence will be assessed via TFV-DP levels in DBS samples ($n \geq 20$ per treatment arm). TFV-DP data will be dichotomized into high levels (≥ 700 fmol/punch) vs low levels (< 700 fmol/punch) and the difference in proportion of high levels of TFV-DP between treatment arm will be estimated using chi-square or Fisher's exact test at both 3 and 6 months. In a separate analysis, we will keep TFV-DP as a continuous variable and examine differences between control and intervention groups using T-tests and permutation tests. Second, at 3 and 6 months, we will use the validated 3-item self-report adherence measure developed by Wilson and his colleagues.²³ T-tests will compare the mean adherence score between intervention and control arm at 3 and 6 months. Permutation tests will also be used to test for treatment group differences, since they do not require distributional assumptions and are typically more robust.

6. REFERENCES:

1. Centers for Disease Control and Prevention. HIV Surveillance Report, 2016. 2017.

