2.3. Eligibility Criteria

Inclusion criteria:

- 1) Prescribed PrEP by a healthcare provider;
- 2) Self-reported 18-29 years of age;
- 3) Assigned male at birth;
- 4) Current male gender identification;
- 5) Gay, bisexual or other non-heterosexual identity or has had sex with a man in the past year;
- 6) HIV negative (HIV negative test in the past 3 months)

- 7) Either started or restarted PrEP in the past 30 days or started PrEP more than 30 days ago and self-reports not always taking PrEP in the past 30 days;
- 8) English-speaking (as the intervention will be built in English);
- 9) Able to meet with project staff at baseline and follow-up visits;
- 10) Regular access to SMS or the internet, either through a mobile device, tablet computer, and/or desktop or laptop computer.

Additional exclusion criteria:

- Not prescribed PrEP by a healthcare provider;
- HIV positive (by a reactive HIV antibody or detectable HIV RNA level);

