2.7. Study Visit Procedures

Study candidates, whether referred by PrEP clinic staff or self-referred from recruitment materials, will be assessed for potential eligibility through a self-directed online screening survey, or through research staff who can assess eligibility by telephone or by assisted participants with completing the online survey. All interested candidates will then undergo a study visit, during which their eligibility will be confirmed followed by informed consent. After consent procedures, participants will complete a computer-assisted baseline survey and complete enrollment visit procedures.

After enrollment, participants are randomized 1:1 to either the intervention (PrEP iT! + usual care) or control (usual care) arm. All participants will be provided usual PrEP educational information encouraged to attend their regular healthcare visits. Participants randomized to the intervention arm will be guided through setting up their user account and user profile, provided with basic training on how to navigate and use intervention components, and given the opportunity to ask questions.

Both control and intervention participants will be offered an optional blood draw at their enrollment and 6 visits. Blood samples and the information collected may be used by the study sponsor, its research partners or companies for additional testing of Tenofovir and metabolites. At the end of this study, these samples may be held in storage by Hennepin Healthcare Research Institute for up to 20 years. After 20 years, the samples will be destroyed. Participants can request that their samples be destroyed at any time by writing to investigators.

YMSM will undergo a follow-up assessment at both 3- and 6-month visits. The follow-up visits include ascertainment of clinical information that was conducted as part of usual PrEP care (e.g., repeat testing for HIV and other STIs), completion of a computerized survey assessment, and collection of a dried blood spot specimen for the TFV-DP analyses. If visit is in person, a finger prick will be done to collect several drops of blood. If visit is online, a self-collection kit will be mailed to participants home where they collect blood by pricking their finger, and then mailing the blood sample to a lab in a pre-paid mailer. See Clinical Management below for procedures for procuring care for diagnoses or disease events that are identified during study conduct.

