A complete list of study visit procedures, data collection, and evaluations performed at Screening, Enrollment and/or Follow-up study visits is listed below in **Table 2**.

Table 2: Study Visit Procedures and Evaluations

Measure	Screening Assessment	Enrollment Visit	3 Month Visit	6 Month Visit
RCT online screener	X			
Informed Consent		X		
Verification of eligibility		X		
Randomization		X		

Participant and clinical data				
Demographic information	X			
HIV status	X	X	X	X
PrEP medications and strategy		X	X	X
Medical history		X	X	X
Clinical labs		X	X	X
Disease or clinical events		X	X	X
Surveys Items/Scales				
Demographics and Baseline Characteristics		X		
Technology Use Questions		X	X	X
eHealth Literacy		X	X	X
HIV Negative Cascade		X	X	X
U=U Questions		X	X	X
Substance Use		X	X	X
Sexual Risk Behavior		X	X	X
Mental Health		X	X	X
Social Support		X	X	X
Technology Use Questions			X	X
Intervention Acceptability			X	X
Exit Interview				X
Specimen collection				
Dried Blood Spot Collection		X	X	X
Blood for Storage		X		X

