Tenofovir (TFV) is a primary component of the PrEP medication, and TFV drug levels will be assessed in a random subset of participants (≥50%) to evaluate objective adherence. TFV is phosphorylated in cells to TFV-diphosphate (TFV-DP), which is both pharmacologically active (in relevant cells) and demonstrates a longer intracellular half-life compared with the parent drug in plasma. The presence of TFV-DP in red blood cells (RBCs) can be measured within a dried blood spot (DBS) analysis. TFV-DP levels in DBS will be measured by [name] Laboratory using established standardized protocols.²¹ Through this methodology, estimates can be made of the number of TDF doses taken over a 7-day period.

Blood collection for DBS sample acquisition can be done via venipuncture or fingerstick. Blood drawn by venipuncture should utilize an EDTA collection tube, and processed within 60 minutes of collection by applying the blood directly onto the designated circle on the collection card. Blood from finger stick should be spotted on the card immediately by touching the blood drop to the card without pressing the finger to the card. After blood is applied, the cards are air dried for several hours (overnight is acceptable) and then stored in low gas-permeability bags. DBS card specimens are then stored under frozen conditions (20°C, or -80°C) until analysis. Specimens will be labeled with PID, study, date, and visit type, but will not include any individual identifying information. Please see the study MOP for additional step by step details on blood collection, processing to DBS cards, storage and shipping instructions.

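### The enrollment dried blood spot has no stated role in the TFV-DP analysis; adjusting for it could gain precision and guard against chance imbalance at about 20 per arm

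*Combined protocol and SAP*

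**What the plan says.** - **Collection.** In Table 2 (section 2.7) the row "Dried Blood Spot Collection" is marked at the enrollment, 3-month and 6-month visits. The text of 2.7 mentions the card only for the follow-up visits, which include "collection of a dried blood spot specimen for the TFV-DP analyses". For online visits, "a self-collection kit will be mailed to participants home where they collect blood by pricking their finger".
- **Assay.** Section 3.5 says that "TFV drug levels will be assessed in a random subset of participants", at least half of them. It does not say which visits' cards are assayed.
- **Analysis.** Section 5.3 says "Objective adherence will be assessed via TFV-DP levels in DBS samples", with at least 20 per arm. The 700 fmol/punch dichotomy is tested by chi-square or Fisher at 3 and 6 months. For the continuous level the plan will "examine differences between control and intervention groups using T-tests and permutation tests"; that sentence names no visit. No covariate, change score or repeated-measures model appears.
- **Population and allocation.** Criterion 7 in section 2.3 reads "Either started or restarted PrEP in the past 30 days or started PrEP more than 30 days ago and self-reports not always taking PrEP" over the past 30 days, with no upper limit on time since starting. Section 5.2 stratifies randomization by age group only, and age does not enter the analysis either.

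**The concern.** TFV-DP is the trial's only objective adherence measure, and criterion 7 makes exposure at entry heterogeneous. A recent starter's level depends partly on days on drug, while an earlier starter's depends on how imperfect his adherence has been. Neither PrEP history nor entry level is a stratification factor, so in some 20 assayed participants per arm only chance balances them.

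If the enrollment level predicts the later level, an unadjusted comparison carries avoidable error. A chance difference at entry would also pass into the estimated effect of the app. Section 2.1 says the pilot is meant to inform a later trial, so a distorted estimate could carry into that trial's design.

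**Working it through.** **1. The plan's own figures (section 5.1).** I take two-sided 5% and 80% power; the plan does not state sidedness.
- Pooled chi-square, 20 per arm: against 40% in controls, 80% power is reached at 82.0%, so RR = 0.820/0.40 = 2.05. Against 30% it is reached at 73.0%, so RR = 0.730/0.30 = 2.43. These agree with the stated 2.0 and 2.4 to one decimal.
- Self-report score, 40 per arm, SD 20: detectable difference 0.634 × 20 = 12.7 units, as stated.

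Both are unadjusted calculations. The plan gives no figure for continuous TFV-DP.

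**2. Continuous TFV-DP as planned.** With 20 per arm, the SE of the difference is √(2/20) = 0.316 SD with 38 df. The noncentral t gives a detectable difference of 0.909 SD.

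**3. Chance imbalance at entry.**
- The baseline mean difference also has SD 0.316. It exceeds 0.3 SD in either direction in 34% of trials and 0.5 SD in 11%.
- For a binary entry characteristic with prevalence p, the SD of the between-arm difference is √(2p(1−p)/20) = 0.145 to 0.158 for p = 0.3 to 0.5 (assumed). Exact binomial probabilities of a gap of at least 4 in 20 are 22.6%, 25.8% and 26.8% for p = 0.3, 0.4 and 0.5.
- The unadjusted estimate moves by r times the baseline difference, where r is the baseline to follow-up correlation. In 20,000 simulated trials per value of r, those with a baseline difference above 0.5 SD favouring the intervention had unadjusted estimates off by 0.18, 0.32 and 0.44 SD for r = 0.3, 0.5 and 0.7. The ANCOVA estimates were off by about 0.

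**4. Precision with adjustment.** With k covariates and n per arm, the variance is (2/n)(1−r²)[1 + k/(2n−3−k)] on 2n−2−k df. The bracket charges for estimating the covariate effects. Covariates after the first are assumed to explain nothing further, which is the unfavourable case. The documents do not give r.

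| Assumed r | 20/(1−r²) per arm | k = 1 | k = 2 | k = 3 |
|---|---|---|---|---|
| 0.2 | 20.8 | 0.90 | 0.92 | 0.93 |
| 0.3 | 22.0 | 0.88 | 0.89 | 0.91 |
| 0.5 | 26.7 | 0.80 | 0.81 | 0.82 |
| 0.7 | 39.2 | 0.66 | 0.67 | 0.68 |

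The last three columns are detectable differences in SD, against 0.91 unadjusted.

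**5. Cost of dropping men without a baseline.** With k = 2, losing 1 of 20 per arm at r = 0.3 gives 0.92 SD, and losing 4 of 20 at r = 0.5 also gives 0.92 SD. Either loss more than cancels the gain.

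**The case against.** The strongest reply is that nothing here is an error. Unadjusted t, chi-square, Fisher and permutation tests are valid under randomization, and chance imbalance is already within the 5% error rate. TFV-DP is a secondary outcome of a pilot whose primary outcomes are feasibility and acceptability. The gain depends on a correlation the documents do not give, and that correlation may be weak in recent starters, whose entry level partly reflects time on drug. All of this stands. It limits the point to efficiency and to error in the particular sample drawn; it does not remove the case for using a card that is already scheduled.

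Three stronger readings are tempting but unsupported:
- A reader might infer that the enrollment card is certainly never used. Section 5.3 only fails to give it a role. The visit text omits it, and section 3.5 does not say which cards are assayed. The use is unspecified.
- A reader might infer that the planned tests are biased or have an inflated type I error. Over repeated randomization they are neither.
- Section 1.1 describes protective levels as at least 4 doses a week, and 4/7 × 30 = 17.1. A reader might therefore infer that an eligible man taking 18 or more of 30 doses already exceeds 700 fmol/punch. The documents never link 700 to 4 doses a week, so this cannot be concluded.

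The remedy also has practical limits. Table 2 puts consent and randomization in the same enrollment visit. For an online enrollee, a card taken before allocation would therefore need a kit sent before consent, or a split visit.

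**Conclusion.** The point holds as a moderate-priority improvement. The plan schedules an enrollment specimen and gives it no stated analytic role, in a small subset with mixed PrEP history and no stratification on that history. Adjustment would lower the detectable difference from 0.91 SD to about 0.88-0.89, 0.80-0.81 or 0.66-0.67 SD at assumed correlations of 0.3, 0.5 or 0.7 with one or two covariates. At 0.2 there is essentially no gain. With three covariates, the precision gain at 0.3 also disappears if the second and third explain nothing. Protection against a chance baseline difference grows with the same correlation. The sizes rest on the assumed correlation, one common value across both PrEP-history groups, and 20 assayed per arm with complete data.

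**What to change.** In section 5.3:
1. State that enrollment cards are assayed for the same random subset as the 3- and 6-month cards.
2. Analyse continuous TFV-DP at 3 and at 6 months by ANCOVA with enrollment TFV-DP, PrEP-start group (30 days or less, or more than 30 days) and age stratum as covariates. Run the permutation test on the adjusted statistic.
3. Keep every randomized, assayed participant. Handle a missing baseline by mean imputation with a missing indicator, or by a constrained longitudinal model, and do not drop the participant.
4. Keep the planned 700 fmol/punch test. Any result stratified by baseline level should be supplementary and descriptive, because the strata will be very small.
5. Record each baseline card's date relative to randomization. Take it before allocation is revealed where feasible, and treat clearly later cards as missing baseline under item 3.

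Cost: one extra assay per subset member on cards already scheduled. That is at least 40 (half of 80) and at most 80. The extra covariates use two or three degrees of freedom, and a missing indicator would use one more. Online enrollments may need a change in procedure if the card is to precede allocation. If the true correlation is 0.2 or lower, the adjusted analysis could be slightly less precise than the planned one.
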